6.2.2 Enrollment, Baseline, and/or Randomization

6.2.2.1 Enrollment

Once the candidate has met screening eligibility criteria, and signed the written ICF for study procedures, she will be considered enrolled in the study. Her enrollment date will be the date she signs the ICF. The participant's enrollment date will be recorded on the Enrollment Log. Participants will be enrolled during months 10-47 of the study. Not all participants who enroll will progress to randomization (due to screen failures and those who actively withdraw from the study), we anticipate enrolling individuals as needed at Baylor University to achieve our randomization goal of 131 participants randomized.

6.2.2.2 Baseline Assessments

Demographic Questionnaire & Health History Intake

The Demographic Questionnaire & Health History Intake is a brief intake questionnaire developed to capture participant characteristics, including age, race, ethnicity, education and similar demographics, time since first postmenopausal, history of breast cancer, and will be used to document no current use of alternative treatments for hot flashes.

Hot Flash Daily Diary

A Hot Flash Daily Diary will be used to measure the primary outcome of hot flash score. Participants will be asked to complete the Hot Flash Daily Diary every day for 6 weeks to measure the daily frequency and severity (mild, moderate, severe, and very severe) of hot flashes. Each level of severity is given a value; mild = 1; moderate = 2; severe =3; very severe = 4. Participates will rate the severity of each hot flash as they experience it and record it in their daily diary. A total hot flash score will be calculated for each participant (product of frequency x severity). For example, a woman with 3 mild and 2 severe hot flashes would have a hot flash score of 9 (3x1 = 3 + 2x3 =6). Participants are educated on how to collect hot flash information in real time throughout the course of each day. This process has been successfully used in numerous hot flash studies previously completed by [name] and colleagues^[75] and other investigators including [name]^[38, 39] and has yielded replicable data in trials by different groups who evaluated the same treatments ^[24] A hot flash diary will be provided to the participants at baseline and will be completed during the baseline week. A second diary will be provided for use during weeks 1 through 6 of the intervention period. A third hot flash diary will be used for week 12.

Hot Flash Related Daily Interference Scale (HFRDIS)

Participants will be asked to complete the Hot Flash Related Daily Interference Scale (HFRDIS) during baseline and weeks 6 and 12. This is a 10 item scale that measures hot flash interference.^[82] The HFRDIS asks respondents to rate the degree on a 0-10 scale that the hot flashes interfere with various daily activities as well as overall enjoyment or quality of life. This measure has been shown to be valid and internally consistent, with an alpha of .96.^[82] This will be completed at baseline, 6 and 12 weeks.

PROMISTM Emotional Distress – Anxiety Scale

The PROMISTM Emotional Distress – Anxiety Scale contains 29 items that measure 5 domains of anxiety: 1) affective, 2) cognitive, 3) somatic, 4) behavioral, and 5) need for treatment. Items are scored on a scale from 1-5 with higher scores reflecting more severe anxiety. Like all PROMIS measures, the anxiety scale was developed through rigorous qualitative and quantitative assessment involving expert review, focus groups, and item response theory analysis, and it has shown excellent convergent and discriminate validity with other measures, with a Cronbach's alpha of .95.^[83, 84] This will be completed at baseline, 6 and 12 weeks.

Pittsburg Sleep Quality Index (PSQI)

The PSQI is a 19-item self-report inventory designed to measure sleep disturbance. The 19 items are grouped into 7 subscales: 1) sleep quality; 2) sleep efficiency; 3) daytime dysfunction; 4) sleep latency; 5) sleep disturbances; 6) sleep duration; and 7) use of sleep medication. These seven subscales are scored on a scale of 0-3 with higher scores indicating greater sleep pathology. Previous studies indicate that PSQI total scores are significantly correlated with measures of sleep onset latency, amount of time spent awake after initial sleep onset, and total sleep time as assessed by sleep diary and wrist actigraphy, [85] and alphas for the PSQI range from .70 to .80. [86] A cut point of 5 has been determined through evidence to differentiate sleep disturbance (≤5) from normal sleep. [87] This will be completed at baseline, 6 and 12 weeks.

Subject Global Impression of Change The Subject Global Impression of Change is a 7-point item in which the participant rates the change in hot flashes since beginning the study (ranging from "very much better," "moderately better," "a little better," "about the same," "a little worse," "moderately worse," to "very much worse"). It has been used extensively for determination of minimally clinically significant differences in numerous oncology clinical trials. [88, 89] Four additional investigator-developed questions will be included, of those four, two will ask about satisfaction . This will be completed only at 6 weeks. In addition, two questions about the use of audio recordings are included.

Diurnal Cortisol Rhythm

Each participant will be provided a kit with salivettes for the collection of saliva. Saliva will be collected three times a day over a two consecutive day period at baseline and 6 weeks. Participants will be provided specific directions for the collection of saliva upon awakening, (before getting out of bed), 30 minutes later (before eating, drinking or tooth brushing), and finally at bedtime (around 10 pm, also before tooth brushing) and will be given a Saliva Collection Diary with questions to answer surrounding their saliva collection. Participants will also be instructed to complete Daily Health Behaviors questionnaires during the same two-day period. (This procedure is well established and is considered valid for the measurement of diurnal cortisol rhythm.)^[67, 68]

Cortisol collection is explained in the baseline visit. During the COVID-19 restrictions, this interaction will occur by telephone or video conference. If the participant is unable to demonstrate understanding of the collection process, we will not collect cortisol on that participant in the study. Additionally, if there is any interruption to mail service or to the lab where specimens are banked, this portion of the study will be paused during COVID-19 restrictions.

Measures of Heart Rate Variability

The shift in autonomic balance from sympathetic dominance (stress response) to parasympathetic dominance (relaxation response) is a very likely candidate for the underlying mechanism of the effects of mind-body interventions on vasomotor symptoms. Relatedly, an increasing body of evidence indicates that hot flash events are associated with changes in heart rate variability. [90-92] The Polar V800, a mobile HRV recording device will be worn to collect data over a 24-hour natural ambulatory period as well as two 6 minute supine recordings during the two days of cortisol collection at baseline and 6 weeks. The 24 hr and two 6 minute measurements will be completed (each on separate days) at preand post-trial. The Polar V800 has been shown to have equivalency for the time domain of HRV. [93]

The ambulatory device will be returned to the investigators in a pre-posted mailer immediately following each HRV data collection (i.e., baseline and week 6 endpoint). Data will be downloaded as soon as it is received in the lab, for optimal resolution and to protect privacy. The device will then be cleared of data and available for the next use, which should ensure that study recruitment is not delayed due to a shortage of Polar V800 devices.

Heart rate variability monitoring is explained in the baseline visit. During the COVID-19 restrictions, this interaction will occur by telephone or video conference. If the participant is unable to demonstrate understanding of the collection process, we will not collect heart rate variability on that participant in the study. Additionally, if there is any interruption to mail service, this portion of the study will be paused during COVID-19 restrictions.

Perceived Stress Scale (PSS)

The PSS contains 10 items that measure the degree to which situations in one's life are appraised as stressful. [94] The scale provides the degree to which individuals find their lives to be unpredictable, uncontrollable, and overloaded, as well as measures the current levels of experienced stress. [95] Items are scored on a scale from 0-4 with higher scores reflecting more perceived stress. This measure has been shown to be valid and internally consistent, with an alpha of .83. [94] This will be completed at baseline, 6, and 12 weeks.

[name] Hypnotizability Scale (EHS)

The EHS is a 12-item, research assistant-administered, scale for rating hypnotizability in the general population. Each item is rated pass\fail, with higher scores indicative of greater hypnotizability.

Previous research indicates that the EHS is highly correlated with longer measures of hypnotizability and has excellent reliability with a Cronbach's alpha of .94. [96] This will be administered to participants randomized to the hypnotic intervention group at the randomization visit. The [name] Hypnotizability Scale-Clinical Form (EHS-CF) will be administered during the randomization visit when the randomization visit takes place through telephone or video conference because of COVID-19 restrictions. The EHS-CF a less intensive and shorter version with 9 items compared to the full 12. However, this is not a different scale and provides the same measures we are seeking with a high correlation of .962 between the EHS and EHS-CF. The EHS-CF will allow for an easier implementation of the scale through remote procedures and be more user-friendly for the participants.

Self-Hypnosis Practice Log

Frequency of home practice is thought to be one of the moderators of the *efficacy* of hypnosis interventions^[70] and will be particularly important to collect for this self-administered protocol.^[70] Participants in both groups will be given a log that they will complete daily. The log will provide space to put the date, whether, or not the participant listened to their audio recording, the number of times they practiced (with and without the audio recordings), and

provide a space for comments about any interruptions or barriers to listening to their assigned recording. Between the log and the phone calls, the research assistant will be able to ascertain the degree to which women adhered to the protocol in terms of recording hot flashes in real time and using the audio-recordings as prescribed in the protocol. This will be completed daily during weeks 1 to 6 of the intervention and during week 12.

6.2.2.3 Randomization

Randomization will be assigned after baseline measures have been completed and prior to intervention instruction and administration.

If a period of more than 30 days passes after the screen is complete without the individual coming to the lab for the baseline appointment (except in the case of washout of putative therapies for hot flashes for one month prior to enrollment on study), the initial verbal consent will be considered void, and will need to be repeated and another Inclusion/Exclusion Criteria Screen Checklist will be completed prior to rescheduling the baseline visit. Since randomization will not have taken place, this will not impact accrual numbers but will be counted as a screen failure. Participants who attend the baseline visit and sign the consent form but then never return for their randomization visit will also be considered screen failures, but these women will be replaced to maintain statistical power.

Once randomization has been completed, efforts will be made to ensure that participants enrolled are assisted and encouraged to initiate and complete participation in the materials associated with the condition to which they are assigned.

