Those who are interested in participating in the study will be able to express their interest in doing so via phone, email, or text messaging. Research personnel will then correspond with these interested individuals via phone, email, or text messaging, to schedule a phone screening appointment.

During the phone screening appointment, more study details are provided. If the individual is still interested in participating after this information is provided, verbal consent will be obtained and potential eligibility will be determined using the Inclusion/Exclusion Criteria Screening Checklist which outlines the criteria listed in Sections 4.1 and 4.2. If a woman appears to be eligible, she will be scheduled for a baseline visit (conducted via telephone or video conference during COVID-19 restrictions) where the informed consent process for study procedures, the study purpose, procedures and requirements for baseline data collection will be explained. If she is interested in participating, she will sign the IRB-approved consent form to begin baseline data collection and be assigned a participant study ID number and will be considered enrolled in the study. If the baseline visit is conducted by telephone or video conference, the IRB-approved consent form will either be sent to the participant with a postage-paid envelope for return to the study team or sent through a secure, online platform. The online platform that will be utilized for this study will be DocuSign.

A Screening and Enrollment Log will be maintained at both sites to document eligibility/ineligibility, screen & consent dates, and referral source of each individual screened.

Once baseline data have been collected, a randomization/education visit (conducted by phone or video conference during COVID-19 restrictions) will be scheduled.

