Eligible participants will be randomized to either self-administered hypnosis or self-administered sham white noise hypnosis. Randomization and mailing of appropriate intervention materials will take place several days before the visit if the visit is to take place through phone or video conference due to COVID-19 restrictions. Participants will also have an option of having the appropriate intervention materials shared with them electronically. Education about implementing their assigned arm will take place and for those assigned to hypnosis, the hypnotizability scale will be administered. However, the hypnotizability scale will not be administered if the randomization visit takes place through phone or video conference due to COVID-19 restrictions. Randomization will be

accomplished by the development of equally distributed tables of random numbers by the statistical team.

It is expected that each site (Baylor University and University of MI) will each recruit approximately half of the participants. Accrual will be closely monitored and efforts to randomize an equal number at each site will be made (see Section 9.4). Should accrual and randomization at either site significantly exceed 50% then the accrual percentage will be reduced at the other site accordingly. The randomization list will be kept by the study statistician.

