
10. DATA COLLECTION AND QUALITY ASSURANCE

10.1 Data Collection Forms

Information is provided by participants through written responses to questionnaires, and through physiological measures of cortisol (saliva) and heart rate variability. The self-report measures will be assessed at baseline, week 6, and week 12, with the exception of the Hot Flash Daily Diary which will be completed daily from baseline through week 6, and for one week at week 12. The Self-Hypnosis Practice Log will be completed daily during weeks 1 through 6 of the intervention and again during week 12. Physiologic measures will be collected at baseline and week 6.

Baseline questionnaires will be completed in the lab during the baseline interaction. During the COVID-19 restrictions, the questionnaires will be mailed to the participant with postage-paid envelope for return or sent electronically. The baseline Hot Flash Daily Diary, cortisol collection, and HRV data will be collected at home during the 7 days following the baseline interaction. The baseline hot flash diary, saliva kits and HRV monitor will be given to the participant at the baseline interaction (or mailed to the participant during the COVID-19 restrictions) with comprehensive education about the data collection. The HRV monitor will be worn for the designated time during the two days of cortisol collection. A second interaction within 30 days of the baseline data collection will be scheduled and serve as the

randomization/education interaction. At this visit, participants will be given a Toolkit which will include:

- Intervention materials
 - o weekly education/instruction booklets and audio recordings
- Data collection forms
 - Hot Flash Daily Diaries
 - o Self-Hypnosis Practice Log
- Questionnaire booklets
 - o a compilation of all outcome questionnaires for data collection at Weeks 6 and 12
- Return-addressed mailers (for the return of study materials and data forms)

In the event that the randomization/education visit must take place through telephone or video conference due to COVID-19 restrictions, the Toolkit, containing the appropriate intervention materials, will be mailed or sent electronically to the participant prior to the randomization/education visit. Then, the participant will have these materials prior to the randomization/education visit, and these materials can be discussed in detail during the interaction.

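### The screen-failure rule turns on attending the randomization visit, but for remote visits allocation comes first, so the rule as worded conflicts with intent-to-treat

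*Combined protocol and SAP*

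**What the plan says.** **Timing.** Section 6.2.2.3 places randomisation after the baseline measures and before any instruction in the intervention. Section 4.3 says: "Once baseline data have been collected, a randomization/education visit (conducted by phone or video conference during COVID-19 restrictions) will be scheduled". For in-person visits the recordings and toolkit are handed over at that visit (Sections 3 and 10.1). For remote visits Section 4.3 reverses the order: "Randomization and mailing of appropriate intervention materials will take place several days before the visit if the visit is to take place through phone". The same sentence extends this to video visits held because of COVID-19 restrictions. Section 10.1 agrees that in this case the toolkit with the intervention materials "will be mailed or sent electronically to the participant prior to the randomization/education visit".

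**Screen failures.** Section 6.2.2.3 describes two kinds. The first is a woman who lets more than 30 days pass after screening without coming to the baseline appointment: "Since randomization will not have taken place, this will not impact accrual numbers but will be counted as a screen failure". The second is a woman who attends baseline and signs the consent form. Such women, if they "never return for their randomization visit will also be considered screen failures, but these women will be replaced to maintain statistical power". The next paragraph moves to the period after allocation: "Once randomization has been completed, efforts will be made to ensure that participants enrolled are assisted and encouraged to initiate and complete participation".

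**Counts.** Section 6.2.2.1 explains the gap between enrolled and randomised women: "Not all participants who enroll will progress to randomization (due to screen failures and those who actively withdraw from the study". It sets recruitment at Baylor "to achieve our randomization goal of 131 participants randomized".

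**Analysis set.** Section 9.3 (Treatment Assignment Procedures) includes everyone randomised in the analysis. Section 9.7 repeats this irrespective of non-compliance or withdrawal, and Sections 9.1 and 9.2 also commit to intent-to-treat. Section 8 keeps randomised women who stop the intervention in follow-up to week 12, with their permission.

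**The concern.** Status after allocation should depend on allocation alone. The second screen-failure rule depends on attendance. In person the two coincide, because a woman who misses the visit has not been given an arm. On the remote pathway they separate: a woman can be allocated, be sent her recordings, and then never attend. The rule gives her a pre-randomisation label and calls for someone else in her place.

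The randomised count is at stake. It is the basis of the recruitment goal, the intent-to-treat set and the Section 9.7 comparison of women with and without 6-week data. A site that followed 6.2.2.3 to the letter could log an allocated woman as a screen failure and leave her out of that count. The loss would come after allocation, the staff who randomise and educate are unblinded (Section 6.2.3, Blinding), and she may already hold recordings that differ by arm (Table 3). Dependence on arm is therefore possible, although Section 5.1.2 presents both arms to participants as self-administered hypnosis programs, which reduces that risk.

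**Working it through.** **1. Which women are affected**

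| Woman who never attends the randomization visit | Allocated? | Status in 6.2.2.3 | Status in 9.3 and 9.7 | Consistent? |
|---|---|---|---|---|
| In-person pathway | No | Screen failure, replaced | Not in the set | Yes |
| Remote pathway, lost before allocation | No | Screen failure, replaced | Not in the set | Yes |
| Remote pathway, lost after allocation | Yes | Screen failure, replaced | In the set | **No** |

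Only the third row conflicts. It needs a completed baseline, an allocation made for a remote visit, and then no attendance.

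**2. Whether the text settles the third row**

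- The reason given for the first kind of screen failure is that no randomisation has occurred. The second kind is joined to it by the word *also*, but carries no such condition, and in the third row the reason is untrue.
- Section 6.2.2.1 treats screen failures as women who do not reach randomisation. That shows the intent, but does not amend the rule.
- One could read *return* as coming back in person. However, Section 4.3 and the hypnotizability-scale text in 6.2.2.2 use *randomization visit* for remote visits too.
- Sections 9.3 and 9.7 keep her in the analysis if she is recorded as randomised. They do not say that they override a screen-failure classification.

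**3. How many women**

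The documents give neither the share of remote visits nor the share of allocated women who miss them. Women affected = N × x, where x is the affected share of all randomised women. N is 232 (Section 9.3), or 131 + 116 = 247 if Michigan randomises 116 and Baylor the 131 of Section 6.2.2.1.

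- Per 1%: 232 × 0.01 = 2.3; 247 × 0.01 = 2.5.
- On assumed rates, for scale only (25% to 100% of visits remote, 1% to 5% of women allocated for them never attending), x runs from 0.25 × 0.01 = 0.0025 to 1.00 × 0.05 = 0.05. That is 0.6 to 11.6 women of 232, or 0.6 to 12.4 of 247.

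**4. Whether power is touched**

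The plan's own figure first: effect size 0.41, alpha 5% (two-sided assumed, since the plan does not say), power 80%, equal arms. A t test needs 94.35 per arm, so 95 per arm and 190 in total. Then 190 / (1 − 0.18) = 231.7, rounded up to 232. Both of the plan's figures reproduce.

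Under the literal rule the non-attenders are replaced, so 232 women still attend and 232 × 0.82 = 190.2 still complete. The rule leaves planned power where it was.

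**The case against.** The best defence is that the rule, read in context, covers only unallocated women. The sentence before it presupposes that no randomisation has occurred, the paragraph after it deals with randomised women, Section 6.2.2.1 uses the term in the same sense, and the intent-to-treat commitment is made repeatedly. Allocations also leave a trail: numbered envelopes (Section 3) and case assignment spreadsheets kept by the statistician (Section 9.3). Attendance is largely a matter of fact, and the Manual of Procedures, which is not available here, may define the point of randomisation. Nearly all of this stands. It makes actual exclusion only a possibility. It does not mend the rule, which still gives the wrong status to the one group it overlooks.

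A reader might infer more than the documents support:

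- *That the plan drops randomised women from the analysis.* No section says so, and 9.3 and 9.7 say the opposite.
- *That the rule costs power.* With an assumed 5% never attending on top of a full 18%, 232 × 0.95 × 0.82 = 180.7 women complete and power is 0.78. That describes keeping the non-attenders without outcomes and adding nobody. The rule replaces them.
- *That leaving them out inflates the effect.* At the same assumed 5%, an effect of 0.41 instead of 0.41 × 0.95 = 0.39 requires non-attending hypnosis women to have observed outcomes showing no benefit. Most of those outcomes would be missing and multiply imputed under Section 9.7, so the contrast does not measure this flaw.
- *That classification will differ by arm.* The route exists, but nothing in the documents shows that it would happen or in which direction.

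**Conclusion.** The point holds as an inconsistency, wrong as written and minor. On the remote pathway, Section 6.2.2.3 makes an allocated woman who never attends a replaceable screen failure, while Sections 9.3 and 9.7 place her in the intent-to-treat set. The sections must be reconciled, and the surrounding wording indicates that intent-to-treat is what the plan means.

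The number affected cannot be determined from the documents and is probably small. The range in the working rests on assumed rates with no source in the plan. No power or effect-size loss is attributed to the rule. The finding itself rests only on the order of events in Sections 4.3 and 10.1 and on the absence of an exception in 6.2.2.3. Confidence is high for the mismatch in the text, and much lower for any consequence in practice.

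**What to change.** Add to Section 6.2.2.3:

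> A woman is randomised when her allocation is made (envelope opened). Screen-failure status applies only before that point. A woman allocated for a remote visit who never attends stays in the ITT set, is followed for outcomes with her permission, and is reported by arm as attrition.

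This agrees with Sections 6.2.2.1, 8, 9.3 and 9.7. Recruiting additional women to protect power remains possible, provided that the allocated women are kept.

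The cost is one short paragraph, slightly higher recorded attrition and a few more imputed outcomes. These losses may fall outside the planned 18%, because the Missing Data text in Section 9.7 defines that figure on women who start treatment, and a woman who never attends her education visit has arguably not started. Imputation alone would not correct a loss that depended on arm. The gain is a correct denominator, by-arm reporting, and whatever outcomes follow-up obtains.
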